3.1 STUDY OUTCOME MEASURES	10
4. PARTICIPANT ENTRY	11
4.1 INCLUSION CRITERIA	11
4.2 EXCLUSION CRITERIA	11
4.3 WITHDRAWAL CRITERIA	11
5. ADVERSE EVENTS	11
5.1 DEFINITIONS	11
5.3 REPORTING PROCEDURES	12
6. ASSESSMENT AND FOLLOW-UP	13
7. STATISTICS AND DATA ANALYSIS	13
8. REGULATORY ISSUES	13
8.1 ETHICS APPROVAL	13
8.2 CONSENT	14
8.3 CONFIDENTIALITY	14
8.4 INDEMNITY	14
8.5 SPONSOR	14
8.6 FUNDING	14
8.7 AUDITS	14
9. STUDY MANAGEMENT	15
10. PUBLICATION POLICY	15
11. REFERENCES	15
12. APPENDICES	17

GLOSSARY OF ABBREVIATIONS

EPO	Erythropoietin
DARBE	Darbepoetin alfa
NAA	N-acetylaspartate
MR	Magnetic resonance
HIE	Hypoxic Ischemic Encephalopathy
NE	Neonatal encephalopathy
MRS	Magnetic resonance spectroscopy
LAC	Lactate
U	Units
KG	Kilograms
LMIC	Low and middle-income countries
µG	Micrograms
IV	Intravenous
SNR	Signal to Noise Ratios
EEG	Electroencephalography

STUDY SUMMARY

TITLE Erythropoietin and Darbepoetin in Neonatal Encephalopathy (EDEN) study

DESIGN 3 arm open label pilot randomised controlled trial.

AIMS To examine the physiological effects of erythropoietin (Epo) and Darbepoetin alfa (Darbe) therapy on proton magnetic resonance spectroscopy thalamic N-acetylaspartate (NAA) level in babies with neonatal encephalopathy undergoing cooling therapy.

OUTCOME MEASURES

Phase 1

Primary outcome

Optimization of the signal to noise ratios (SNR) for MR spectroscopy at 1.5Tesla and 3Tesla, using clinical acceptable scan duration at 1.5 Tesla.

Phase 2

Primary outcome

Mean (SD) of thalamic NAA level in babies treated with Epo and Darbe when compared with untreated infants for predicting adverse neurodevelopment.

Secondary outcome

Number of babies in whom thalamic NAA level could be accurately quantified in 3Telsa and 1.5Tesla MR scanners.

POPULATION 20 Adult Healthy Volunteers
220 newborns with hypoxic ischemic encephalopathy.

ELIGIBILITY

Phase 1: Adults

Inclusion Criteria

1. >18 years old.

Exclusion Criteria

1. Adults with disease.
2. Adults with metal implant fitted, such as a pacemaker or artificial joint
3. Pregnancy.

Phase 2: Infants

Inclusion Criteria

1. Age \leq 24 hours
2. Birth-weight $>$ 1.8 kg
3. Gestation \geq 36 weeks
4. Need for continued resuscitation at 10 minutes after birth and/or 10 minutes Apgar score $<$ 6
5. Cooling therapy initiated for neonatal encephalopathy within 6 hours of age as a part of standard clinical care, with an intention of continuing for 72 hours.

Exclusion Criteria

1. Major life-threatening congenital malformation.
2. Concomitant participation in other research projects

DURATION 3-year recruitment followed by a neurodevelopmental assessment between 18 and 24 months after birth.

1. INTRODUCTION

1.1 BACKGROUND

Neonatal Encephalopathy and therapeutic hypothermia

Birth asphyxia related brain injury (hypoxic ischemic encephalopathy; HIE) occurs in 2.6 (95% CI 2.5 to 2.8) per 1000 live births in the UK, and is the most common cause of death and neurodisability in term babies^{1,2}. The economic burden to the treasury on support costs of neurodisability from HIE is massive (£4 billion per year). In addition, birth asphyxia related (obstetric) claims accounted for almost half of the NHS litigation expenses in 2016/17 (approx. £2 billion), increasing by 15% from the previous year. It has been reported that the NHS cost to meet the complex life-long care needs of babies born with brain damage could be soon over £20m per child, and this situation is unsustainable to the NHS.<https://news.sky.com/story/record-rise-in-babies-born-with-brain-damage-sees-nhs-compensation-bill-soar-10991025>. The UK Government has recently (October 2016) announced that reducing birth asphyxia related costs is a priority area for the Government. <https://www.gov.uk/government/news/improving-the-safety-of-maternity-care-in-the-nhs>

The only effective treatment for HIE is whole body cooling, with an estimated saving of £100 million per annum³ to the UK economy, since its introduction as a standard therapy in the NHS in 2007. Cooling therapy has substantially improved the outcomes of babies with HIE in the past decade. However, unacceptably high rate of adverse outcomes are still seen in cooled babies with moderate or severe HIE: death 28% (range 24–38); cognitive impairment 24% (range 21–25); cerebral palsy 22% (range 13–28); epilepsy 19% (range 15–24); cortical visual impairment 6% (range 1–10), with combined death or moderate/severe disability 48% (range 44–53)⁴, and hence better treatments and further optimisation of cooling therapy is required.

A key roadblock in clinical translation of over 15 highly effective neuroprotective treatments in animal models⁵ is the long delay between the intervention and outcome assessments in HIE. i.e. the earliest age at which neurodevelopmental outcome can be accurately assessed is 18 months. Hence, despite having over 2 dozen highly effective treatments in animal models, no further neuroprotective drugs in HIE have been introduced into the NHS in the past 10 years.

Magnetic resonance biomarkers to accelerate clinical translation

We undertook a meta-analysis of all cerebral MR biomarkers for prediction of long term adverse neurodevelopmental outcome following NE⁷; the most robust predictor was derived from basal ganglia or thalamic proton MR spectroscopy (MRS), and is the ratio of the metabolites lactate and N-acetyl aspartate (Lac/NAA).

However, these data were based on small single-centre studies, in encephalopathic infants before the introduction of therapeutic hypothermia into routine clinical practice. Furthermore, there were limited data on absolute quantification of metabolite concentrations, which offer more specific surrogate outcome measures ideally suited to multi-centre trials.

We subsequently developed cross platform 3Tesla MR spectroscopy sequences and then conducted a large prospective study to examine the prognostic accuracy of MR biomarkers in a multi-country setting (8 tertiary hospitals in the UK and USA) involving all common scanner makes (Siemens, Philips and GE). These data showed that thalamic N-acetyl aspartate levels (NAA) at 1 week predicted neurodevelopmental outcomes at 2 years with an area under curve of 0.99⁸. An accompanying commentary in the Lancet Neurology (Nov 2018) by leading academics explains

how this biomarker as a surrogate outcome measure in next generation clinical trials can accelerate clinical translation of new neuroprotective drug therapies⁹.

While MR spectroscopy at 3Telsa is ideal for neonatal brain imaging, only few centres in the UK have 3T MR scanners. Many NHS hospitals continue to use 1.5 Tesla scanners and are not able to participate in neonatal neuroprotection trials. *Hence, it essential to develop comparable MR spectroscopy sequences at 1.5 Tesla for conducting multicentre studies in the UK.*

[figure not shown]
Erythropoietin therapy in neonatal encephalopathy

Erythropoietin (Epo) is a widely used and FDA approved drug for treating anaemia in various age groups, including newborn infants. Over 34 randomised controlled trials recruiting over 3500 premature babies have reported the safety and efficacy of Epo therapy for anaemia of prematurity.

Several recent reviews have highlighted Erythropoietin as one of the most promising therapies to augment hypothermic neuroprotection. Epo has both acute effects (anti-inflammatory, anti-excitotoxic, anti-oxidant, and anti-apoptotic) and regenerative effects (neurogenesis, angiogenesis, and oligodendrogenesis) essential for the repair of injury and normal neurodevelopment in animal models⁵. Of the long list of highly effective drugs in animal models of HIE and early clinical studies, Epo is the most promising. It is the only drug with a long therapeutic window (at least 24 hours), is widely available, inexpensive, and can be easily administered on a once a day dosing schedule. It has been extensively evaluated in large randomised controlled trials for anaemia of prematurity and has a proven safety profile in newborn infants¹⁰.

Furthermore, pharmacokinetics of erythropoietin in term encephalopathic babies undergoing cooling therapy is well studied. A dose of 1000 U/kg every 24 hours provides adequate levels associated with optimal neuroprotection in pre- clinical models and are very well tolerated¹¹.

We conducted a systematic review of all the randomised controlled trials of Epo in HIE published to date. The pooled data suggest Epo reduces death or disability at 12 months or more after NE (risk ratio 0.61 (95% CI 0.48 to 0.78). However, the individual studies were small and of poor quality, and all except one study examined the efficacy of Epo monotherapy in low and middle-income countries (LMIC), without the adjunct use of therapeutic hypothermia.

Darbepoetin

Darbepoetin, a long acting erythropoiesis stimulating agent, has dual erythropoietic and potential neuroprotective effects. It has been extensively evaluated in newborn infants for its erythropoietic effects. The DANCE study (Darbepoetin administered to neonates undergoing cooling for encephalopathy) randomised 30 term infants with moderate to severe HIE to placebo (n=10), 2 µg/kg Darbe (n=10) or 10 µg/kg Darbe (n=10) IV. At 2 and 10 µg/kg Darbe, t_{1/2} was 24 and 32

hours. A dose of 10 µg/kg dose achieved an AUC in the neuroprotective range, and a terminal t1/2 of 53.4 hours when compared to the 2 µg/kg dose. No side effects attributable to Darbe were reported.

Safety profile of EPO and Darbe

Erythropoietin stimulating Agents (ESA) are glycoprotein regulating red blood cell production and are used to treat anaemia due to chemotherapy, kidney disease, major surgery, or certain treatments in HIV in adult and children.

Most complications of ESAs have been derived from studies in adults. The more common complications of prolonged ESA treatment in adults and children are arthralgia, embolism and thrombosis, headaches, flu-like symptoms, hypertension, skin reactions, stroke, hypertensive crisis, respiratory tract congestion, seizure, thrombocytosis and pure red cell aplasia¹⁵.

Several individual studies have shown a potential trend associating ESA use with increased cancer progression¹⁶⁻¹⁸. Apro et al¹⁹ in systematic review concludes that the balance of current evidence does not support an effect of ESAs on stimulating tumor progression in adults receiving chemotherapy and treated for a minimum of 4 weeks and up to 12 months. A Cochrane review by Tonia et al²⁰ showed that the available data are insufficient to evaluate the effect of ESAs on tumour response.

EPOETIN ZETA	DARBEPOETIN ALPHA
Common or very common Asthenia; dizziness	Common or very common Hypersensitivity; oedema
Uncommon Intracranial haemorrhage	
Rare or very rare Angioedema	
Frequency not known Aneurysm; cerebrovascular insufficiency; hypertensive encephalopathy; myocardial infarction; myocardial ischaemia	

Table 1. Specific complications from Epoetin Zeta and Darbeпоetin Alpha in children.²¹

However, these adverse effects have not been reported in Epo- or Darbe-treated neonates. In clinical trials that evaluated possible undesired side-effects from epo and darbe treatment in term infants found no difference in adverse outcomes or complications, compared to control group, as outlined in Appendix 1. Erythropoietin dosing regimens in neonates for intravenous infusion vary between 250IU/kg to 2500IU/kg, 3 to 7 doses for a maximum of two weeks (Appendix 1). In adults, Epo dosing regimens vary between 50-600units/kg 3 times weekly for a minimum of 4 weeks¹⁵.

An EPO-induced high haematocrit can also cause brain injury²². However, babies with NE usually have lower haematocrits from perinatal events or from frequent blood sampling for clinical monitoring²²⁻²³. Zhu et al²³ compared two groups of term infants affected with NE: 83 received erythropoietin and 84 received conventional treatment. Haemoglobin and reticulocyte levels decreased significantly at 2 weeks after birth in the control group, but this decrease was prevented in the erythropoietin group.

Basegra et al²⁴, in the DANCE study reported that none of the most common complication of prolonged darbe treatment were found in the darbe- treated term infants. And more recently, Juul et al²⁵ randomised 741 preterm infants to high dose erythropoietin versus placebo and found no meaningful differences between groups in any serious adverse events, including those known to occur in adults who receive long-term erythropoietin treatments.

Benefits of the study

The data from this study will provide key feasibility information for future neuroprotection trials. Firstly, the study will inform if multicentric trials using thalamic NAA can be conducted in a setting with both 1.5 Tesla and 3 Tesla MR scanners.

Secondly, this study will provide a Go/No Go signal for a subsequent phase II placebo controlled randomised controlled trial to examine the clinical benefits of Epo on neurodevelopmental outcomes in cooled infants with neonatal encephalopathy.

3. STUDY OBJECTIVES

Phase I: MR spectroscopy sequence development

To develop comparable 1.5 Tesla and 3Tesla MR spectroscopy sequences for obtaining similar thalamic N-acetyl aspartate levels

Objectives

1. To obtain similar signal to noise ratios (SNR) for MR spectroscopy at 1.5Tesla and 3Tesla, using clinical acceptable scan duration at 1.5 Tesla.
2. To compare the thalamic NAA levels in healthy adult volunteers scanned at 1.5 Tesla and 3Tesla MR scanners.

Phase 2: Erythropoietin and Darbepoetin therapy

To examine the physiological effects of erythropoietin or Darbepoetin therapy on proton magnetic resonance spectroscopy thalamic N-acetylaspartate (NAA) level in babies with neonatal encephalopathy undergoing cooling therapy.

Objectives

1. To examine the feasibility of obtaining thalamic NAA levels at 3Tesla and 1.5 tesla MR scanners.
2. To examine the mean values and standard deviation of thalamic NAA levels following erythropoietin or Darbepoetin therapy in babies with neonatal encephalopathy undergoing cooling therapy between 1 to 2 weeks of age.

3. STUDY DESIGN

This study will be conducted in two phases:

Phase 1: This phase will be conducted at Imperial NHS trust and Imperial College London, recruiting 20 healthy adult volunteers over a 2-month period. All volunteers will be scanned at 1.5 Tesla and 3Tesla MR scanners, and the sequences will be optimised to obtained comparable thalamic NAA levels.

Phase 2: This phase will be conducted in 15 tertiary neonatal units in the UK over a 2-year period; 7 with 3Tesla MR scanners and 8 with 1.5 Tesla MR scanner, using the optimised MR spectroscopy sequences.

Babies (>36 week gestation and birthweight >1.8kg) requiring resuscitation at birth will be screened for eligibility, and recruited if there is evidence of acute perinatal asphyxia (metabolic acidosis in cord and/or blood gas (pH<7.15; BE >-12) within 1h of birth; acute obstetric event) AND the need for continued resuscitation or ventilation at 10 minutes and a 10 min Apgar score <6

AND evidence of moderate or severe HIE on an NICHD neurological examination performed between 1 and 6h of birth AND cooling was initiated before 6 h of age. Babies with mild HIE, and those cooled after 6 hours or with life threatening congenital malformations will be excluded.

After informed parental consent, a total of 220 babies with HIE (aged <24 hours) undergoing therapeutic hypothermia will be randomised to one of the following groups

- Arm 1: Erythropoietin (1000 U/kg) IV once a day x 5 doses along with cooling therapy
- Arm 2: Darbepoetin Alpha (10 mcg/kg) IV single dose given less than 24 hours of age along with cooling therapy.
- Arm 3: Cooling only (usual care)

Electroencephalography (EEG)

Babies recruited from Imperial NHS trust will have a 16-channel video electroencephalography (EEG), and those recruited from other centres will have amplitude integrated EEG (aEEG) measurements for the first 80 hours. The video EEG will be acquired and uploaded into a cloud based sever. This system allows a variety of research EEG double reporting options. Neonatal seizures will be classified based on their diagnostic certainty into 5 levels, as defined by the Brighton Collaboration (<https://www.brightoncollaboration.org/peer-review/GAIA-Neonatal-Seizures.html>).

Blood samples

We will collect 0.5ml of blood as soon as possible after birth and again at 80 hours of age from all recruited babies for gene expression studies. The blood (venous or arterial) will be collected in a PAXGENE bottle, at the time of routine clinical sampling, whenever possible.

MR Imaging and spectroscopy

1.5 Telsa and 3 Telsa MR scan using the harmonised sequences will be acquired between 1 to 2 weeks after birth. Briefly this will include T1 and T2-weighted imaging, and diffusion tensor imaging, a single voxel thalamic spectroscopy for absolute quantification of NAA, as reported previously (Lally et al Lancet Neurology Nov 2018). The conventional MR images will be reported using a validated scoring system, and the MR spectroscopy will be analysed using LC model and an in-house motion correction software.

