3.1 STUDY OUTCOME MEASURES

Phase 1:

Primary Outcome Measures

- Similar signal to noise ratios (SNR) for MR spectroscopy at 1.5Tesla and 3Tesla, using clinical acceptable scan duration at 1.5 Tesla.

Phase 2:

Primary outcome measures

- Mean (SD) of thalamic NAA level in babies treated with Epo and Darbe when compared with untreated infants.

Secondary outcome measures

- Number of babies in whom thalamic NAA level could be accurately quantified in 3Telsa and 1.5Tesla MR scanners.

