7. STATISTICS AND DATA ANALYSIS

We expect to recruit at least 60% of the eligible population and to have adequate quality data on the primary outcome for the main trial (i.e. thalamic N-acetylaspartate concentration) in >95% of the recruited babies.

We will use an unpaired t-test to estimate the difference in thalamic/basal ganglia NAA concentration between infants receiving erythropoietin and Darbepoetin alfa.

The standard deviation of [NAA] in the MARBLE study was 0.8. To detect a difference of 0.5 mmol/kg wet weight of [NAA] at 90% power and 0.017 significance, 71 infants will be required for each of the 3 groups for unadjusted analysis. The total sample size is increased to 220 to account for neonatal mortality and any unusable data due to motion artefacts. Data and all appropriate documentation will be stored for a minimum of 10 years after the completion of the study, including the follow-up period.

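### The unadjusted t-test pools NAA from 1.5T and 3T scanners although their agreement is still an open question; a model with field strength and HIE severity would protect it at almost no cost

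*Protocol*

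**What the plan says.** Protocol section 3 (Study Design) places Phase 2 in 15 units, "7 with 3Tesla MR scanners and 8 with 1.5 Tesla MR scanner, using the optimised MR spectroscopy sequences". Babies "will be randomised to one of the following groups", with three arms listed; neither an allocation ratio nor a stratification factor is given.

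Section 7 sizes the trial on a single figure: "The standard deviation of [NAA] in the MARBLE study was 0.8". The calculation is "To detect a difference of 0.5 mmol/kg wet weight of [NAA] at 90% power and 0.017 significance", from which "71 infants will be required for each of the 3 groups for unadjusted analysis". It then says: "The total sample size is increased to 220 to account for neonatal mortality and any unusable data due to motion artefacts". The test it names is an unpaired t-test, with no term for field strength, centre or severity.

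The Phase 1 primary outcome in section 3.1 is "Similar signal to noise ratios (SNR) for MR spectroscopy at 1.5Tesla and 3Tesla". This is not all that Phase 1 does. The second Phase 1 objective compares thalamic NAA in healthy adults between the two field strengths, and section 3 (Study Design) says the sequences will be tuned until NAA levels are comparable, in 20 volunteers scanned on both.

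For Phase 2, the primary outcome is the mean (SD) of thalamic NAA. The background (Benefits of the study) lists whether trials can mix 1.5T and 3T scanners among the things the study will find out. It describes the earlier multicentre work as 3T: "We subsequently developed cross platform 3Tesla MR spectroscopy sequences".

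**The concern.** A pooled t-test treats a value from a 1.5T scanner and one from a 3T scanner as interchangeable. The protocol does not yet claim that they are.

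The Phase 1 primary outcome does not settle the matter. Signal-to-noise ratio describes how noisy a measurement is. Two scanners can be equally noisy and still differ systematically in the level they report. The planned NAA comparison in adults bears on this directly, but it is not the primary outcome, has no stated tolerance and is not tied to how the Phase 2 data are analysed. The Phase 2 secondary outcome counts scans in which NAA could be quantified, so it would not reveal an offset either.

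Two things are at stake. Any remaining offset becomes error variance in the arm comparison. It also enters the reported outcome: the pooled SD is widened, and the pooled mean depends on how many babies happened to be scanned at each field strength. The study is meant to give a go/no-go signal and feasibility data for later trials, so a mean and SD that mix two scanner types would carry forward.

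**Working it through.** **Inputs from the protocol (section 7 unless noted).** Difference 0.5 mmol/kg; SD 0.8; significance level 0.017; power 90%; 71 per arm; seven 3T and eight 1.5T units (section 3, Study Design).

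**Assumed inputs.** The protocol gives no NAA offset between field strengths, no SD for 1.5T and no share of babies by scanner. I take the share of babies at 3T as w = 7/15, equal allocation to arms, a two-sided test, and a range of offsets and 1.5T SDs.

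**Step 1: reproduce the stated size.** The standardised difference is 0.5/0.8 = 0.625. An exact two-sample t-test at two-sided 0.017 and 90% power needs 70.3, so 71 per arm. Power at 71 is 90.3%. The stated figure is correct. A one-sided test would need 61 and does not match.

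**Step 2: pooled variance with two scanner types.** With offset d and SD s at 1.5T:

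pooled variance = w × 0.8² + (1 − w) × s² + w(1 − w) × d², where w(1 − w) = (7/15)(8/15) = 0.249.

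For d = 0.5 and s = 0.8: 0.64 + 0.249 × 0.25 = 0.702, so the SD is 0.838. For d = 1.0: 0.64 + 0.249 = 0.889, SD 0.943. For d = 0 and s = 1.0: (7/15)(0.64) + (8/15)(1.0) = 0.832, SD 0.912.

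**Step 3: power at 71 per arm.** The adjusted column drops the d² term.

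| Offset d (mmol/kg) | SD at 1.5T | Pooled SD | Unadjusted power | n per arm for 90%, unadjusted | Adjusted power |
|---|---|---|---|---|---|
| 0 | 0.8 | 0.80 | 90.3% | 71 | 90.3% |
| 0.25 | 0.8 | 0.81 | 89.5% | 73 | about 90% |
| 0.5 | 0.8 | 0.84 | 87.1% | 78 | about 90% |
| 1.0 | 0.8 | 0.94 | 77.1% | 98 | about 90% |
| 0 | 1.0 | 0.91 | 80.1% | 92 | 80.1% |
| 0.5 | 1.0 | 0.95 | 76.8% | 98 | 80.1% |

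With SD 0.8 at both field strengths, power first falls below 88% at an offset of about 0.43. With no offset, it does so at a 1.5T SD of about 0.86.

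**Step 4: the same effect seen as chance imbalance.** Under simple randomisation the standard error of the between-arm difference in 3T share is √(2 × 0.249/71) = 0.084, or 8.4 percentage points. An offset of 0.5 therefore adds random error of 0.5 × 0.084 = 0.042 mmol/kg to the arm contrast. The contrast's own standard error is 0.8 × √(2/71) = 0.134. Combined, √(0.134² + 0.042²) = 0.141, which equals 0.838 × √(2/71). Added variance and chance imbalance are one loss described in two ways and should not be counted twice.

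**The case against.** The strongest reply has four parts.

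*Randomisation protects the comparison.* This stands. An offset is unrelated to arm except by chance, so the t-test is unbiased. A reader might infer that mixing scanners biases the treatment effect; nothing in the protocol supports that.

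*The power loss is hypothetical.* This also stands. A reader might infer that true power is below the stated 90%. That would need a non-zero offset or a larger SD at 1.5T, and the protocol gives neither. An offset as large as the whole target effect costs about 3 points (90.3% to 87.1%). The 77.1% figure needs an offset twice the target effect to survive harmonisation. If Phase 1 does achieve similar signal-to-noise, one main reason for a larger SD at 1.5T is weakened too.

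*Phase 1 already targets NAA level.* This is true, and it is wrong to say that Phase 1 looks only at noise. What remains is that the comparison is in healthy adults, has no tolerance, and leads to no change in the Phase 2 analysis. It is tempting to answer with a pass/fail gate, for example a 95% CI for the paired difference within ±0.25 from the 20 volunteers. That would not work. If the SD of paired differences were 0.3, 0.5 or 0.8 (assumed), the CI half-width would be 0.14, 0.23 or 0.37, and perfectly matched sequences would pass about 88%, 18% and well under 1% of the time.

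*Covariates belong in the SAP, which is not shown.* This stands in part. The sizing statement does not forbid an adjusted analysis. But the protocol does not leave the method open: it names a t-test. A later adjusted primary analysis would change what the protocol fixes, and is better written there.

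**Conclusion.** The point holds as a recommendation to improve the primary analysis; it does not show an error in the sample size. The protocol fixes an unadjusted test on one SD while scanning at two field strengths whose agreement it has set out to study, and its Phase 1 primary outcome cannot rule out an NAA offset.

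The size depends on quantities the protocol does not give. With no offset and equal SDs nothing is lost. Assumed offsets of 0.25 to 1.0 mmol/kg take unadjusted power from 89.5% to 77.1%, all recoverable by adjustment. A 1.5T SD of 1.0 takes it to 80.1%, not recoverable that way. The effect on the reported mean (SD) is the more direct consequence: any offset widens the pooled SD and ties the pooled mean to the scanner mix, even where power barely moves.

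Two limits apply. That the SD of 0.8 is a 3T figure is an inference, because the protocol does not say that the MARBLE study is the 3T cohort in its background. And HIE severity is recommended as a baseline variable likely to be related to NAA; the protocol gives no basis for claiming a particular gain in power from it.

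**What to change.** 1. In section 7, replace the unpaired t-test with a linear model of thalamic NAA on arm, field strength (or centre) and baseline HIE severity. Field strength follows from the unit, and severity comes from the examination at 1 to 6 hours that eligibility requires. Leave out age at scan, which is fixed only after randomisation. In the same edit, state the arm contrasts: the t-test sentence names Epo against Darbe, while section 3.1 compares treated with untreated babies.
2. Stratify randomisation by field strength or centre, if this is still possible.
3. Report NAA mean (SD) and the arm effect separately for 1.5T and 3T, as a descriptive check.
4. Report the paired 1.5T–3T NAA difference from the 20 volunteers with its 95% CI, without a pass/fail margin.
5. State which field strength the SD of 0.8 comes from, and show power over a range of 1.5T SDs, since adjustment does not protect against a larger one.

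The severity covariate needs settled levels: section 3 (Study Design) excludes mild HIE and section 4.1 admits it, so the two must be reconciled.

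The cost is wording and a randomisation setting, with no extra scans. Field strength and two-level severity use two degrees of freedom, and a third severity level uses one more. Fixed centre effects would use 14, so field strength is the leaner choice.

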4. PARTICIPANT ENTRY

4.1 INCLUSION CRITERIA

Phase 1

Adults >18 years old.

Phase 2

All babies aged ≤ 24 hours, ≥ 36 weeks with a birth-weight >1.8 kg with clinical evidence of encephalopathy (mild, moderate or severe) within 6 hours of birth, along with evidence of an intra-partum asphyxia insult and where cooling therapy encephalopathy within 6 hours of age as a part of standard clinical care, with an intention of continuing for 72 hours.

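### The asphyxia entry rule writes the base-excess inequality against its own term, metabolic acidosis, and the Study Summary and Study Design contradict each other on the resuscitation and Apgar gate

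*Protocol*

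**What the plan says.** The protocol describes Phase 2 entry in three places.

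- **Section 3, Study Design.** Babies are recruited if there is evidence of acute perinatal asphyxia, given in brackets as "metabolic acidosis in cord and/or blood gas (pH<7.15; BE >-12) within 1h of birth; acute obstetric event". In addition they must have "the need for continued resuscitation or ventilation at 10 minutes and a 10 min Apgar score <6". Moderate or severe encephalopathy on examination and cooling begun before 6 hours are also required. This is the only place where a blood-gas criterion appears.
- **Study Summary, Eligibility, Phase 2, inclusion criterion 4.** "Need for continued resuscitation at 10 minutes after birth and/or 10 minutes Apgar score" below 6. Ventilation is not named, and none of the listed criteria asks for a gas result.
- **Section 4.1, Inclusion Criteria, Phase 2.** Encephalopathy within 6 hours of birth, "along with evidence of an intra-partum asphyxia insult". No gas, resuscitation or Apgar threshold is given.

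Study Design places Phase 2 in 15 tertiary neonatal units. Section 7 expects at least 60% of the eligible population to be recruited.

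**The concern.** There are two separate faults. First, base excess becomes more negative as metabolic acidosis worsens. A criterion that asks for a value above -12 therefore selects in the opposite direction from the pH limit beside it and from the term it defines. Second, the Study Summary and Study Design use different connectors for the 10-minute criteria, so the same baby can be eligible under one and ineligible under the other.

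What is at stake is the definition of the trial population. A site that screens from the Study Summary and a site that screens from Study Design would apply different gates, and an eligibility audit could class the same infant as a valid entry or as a deviation. Asphyxia severity plausibly bears on thalamic NAA, the primary outcome, so who is in the trial affects how its mean and SD are read. The expected 60% recruitment also has no fixed denominator while eligibility is stated in conflicting ways.

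**Working it through.** **The plan's own figure.** The point does not depend on the sample size, but section 7 was reproduced first. Inputs: an SD of 0.8 for NAA, which section 7 takes from the MARBLE study; a target given there as "To detect a difference of 0.5 mmol/kg wet weight of [NAA] at 90% power and 0.017 significance"; two-sided testing assumed, since sidedness is not stated. The normal approximation is n = 2(z₁₋α/₂ + z₁₋β)²σ²/δ² = 2 × (2.387 + 1.282)² × 0.64/0.25 ≈ 69 per group. The two-sample t-test gives 70.3, hence 71, which agrees with "71 infants will be required for each of the 3 groups for unadjusted analysis". Nothing below changes that number.

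**Step 1: the gas criterion as printed.** Take two pH values either side of 7.15 and two base-excess values either side of -12, and apply the printed inequality under each possible connector. The last two columns show the same cases with the inequality turned round.

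| pH | Base excess | Printed, both required | Printed, either suffices | Turned round, both required | Turned round, either suffices |
|---|---|---|---|---|---|
| 7.0 | -16 | fails | passes | passes | passes |
| 7.0 | -4 | passes | passes | fails | passes |
| 7.2 | -16 | fails | fails | fails | passes |
| 7.2 | -4 | fails | passes | fails | fails |

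As printed, if pH and base excess are both required, every baby with base excess of -12 or lower fails, including one with pH 7.0 and base excess -16. If either suffices, that baby enters on pH. But a baby with pH 7.2 and base excess -16 fails, while one with pH 7.2 and base excess -4 passes. Under both connectors the base-excess limb works against the stated term.

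**Step 2: the obstetric event.** It is set off by a further semicolon. If it is an alternative route, a baby who fails the gas criterion could still enter through it. If it is a joint requirement, it offers no such route. The text does not say which.

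**Step 3: the 10-minute gate.** Treat resuscitation and Apgar below 6 as present or absent.

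| Resuscitation at 10 min | Apgar below 6 | Study Design | Study Summary |
|---|---|---|---|
| no | no | fails | fails |
| no | yes | fails | passes |
| yes | no | fails | passes |
| yes | yes | passes | passes |

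The two disagree in 2 of 4 combinations. The Study Summary gate is the wider one. Counting ventilation, as Study Design does, does not alter this: any baby passing the Study Design gate has Apgar below 6 and so passes the Study Summary gate.

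**Step 4: does section 4.1 decide?** No. It asks for evidence of an asphyxial insult without a threshold, which is compatible with either of the other two sections.

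**The case against.** The strongest reply is that the intent is plain. The words metabolic acidosis stand in the same phrase, the sites are tertiary neonatal units, and staff may well read the inequality as shorthand for a base deficit over 12. That is fair, and actual exclusions may be fewer than the literal text implies. But it rescues the intent, not the wording against which eligibility would be audited, and it does nothing for the conflict over the 10-minute gate.

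A reader might go further than the documents allow in four ways.

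- **That the rule simply excludes acidotic babies.** This holds for every baby with base excess of -12 or lower only if pH and base excess are both required and the obstetric event is not an alternative route. The semicolons leave both questions open.
- **That three sections define three contradictory asphyxia rules.** On this point section 4.1 is less specific than Study Design and can be read as the general statement that Study Design spells out. The direct contradiction is between the Study Summary and Study Design.
- **That power falls by a known amount.** If 10% to 20% of infants entered under the wider gate with no scope for benefit, the mean difference would fall to 0.5 × 0.9 = 0.45 or 0.5 × 0.8 = 0.40, and power at 71 per arm to 82% or 71%. The arithmetic is right, but the documents give no such share. Nor do they support zero benefit in babies who are all encephalopathic and cooled, and the SD is held at 0.8 although the case mix is supposed to change. Admission of milder cases is also a separate conflict: Study Design excludes mild encephalopathy and section 4.1 admits it.
- **That a 60% feasibility target is compromised.** Section 7 states 60% as an expectation. It is not among the Phase 2 objectives or outcomes.

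Differing practice between sites is likewise a risk that the text creates, not something the protocol reports. Randomisation still protects the comparison between arms.

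**Conclusion.** The point holds as an error and a contradiction in the entry rule, not as missing detail. The base-excess inequality contradicts the term it defines under either connector between pH and base excess. The connectors among pH, base excess and obstetric event are not stated. Study Design and the Study Summary disagree for any baby with only one of the two 10-minute features, and section 4.1 does not resolve it.

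The first two conclusions rest on the printed text read literally; the third does not depend on how the inequality is read. The size in infants is unknown, because the documents do not say how many babies fall between the two gates or have a base excess of -12 or lower. No effect on power or on the figure of 71 per group can be claimed. The consequence is a population that cannot be pinned down, and with it the denominator of the expected 60% recruitment. This should be corrected.

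**What to change.** 1. Make the base-excess inequality in Study Design agree with the protocol's own term, metabolic acidosis.
2. State how pH, base excess and acute obstetric event combine: which are joint and which are alternative.
3. Reconcile the 10-minute criteria, including whether ventilation counts. The choice of connector is the sponsor's; this review does not say which is right.
4. Put the identical full criterion in the Study Summary, Study Design and section 4.1.

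The cost is amendment wording and a matching screening form. The sample-size calculation does not need to change on this account.
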